The PrEvention of post-traumatic contractuRes with Ketotifen I (PERK-I) trial, a Phase II singlecenter randomized clinical trial (RCT) that compared oral Ketotifen Fumarate to a lactose placebo showed that Ketotifen Fumarate was neutral in terms of improving elbow range of motion (ROM)⁶. However, a subgroup of the trial, i.e., those who underwent surgery, indicated that Ketotifen Fumarate improved their range of motion. Therefore, the PrEvention of posttraumatic contractuRes with Ketotifen 2 (PERK-2) trial will assess the effectiveness of Ketotifen Fumarate in increasing the range of motion among surgical patients.

2. Study Objectives

The PERK-2 study aims to demonstrate that Ketotifen Fumarate (2 mg or 5 mg) administered within 10 days of injury is more effective than a placebo in reducing post-traumatic elbow joint contractures in adult participants with elbow fractures and/or dislocations. The efficacy of Ketotifen Fumarate over placebo will be assessed by comparing the difference in elbow range

Patient-Reported Outcome Measures (PROM). Lastly, the study will assess the safety of Ketotifen Fumarate through the reporting of adverse events (AE) and serious adverse events (SAE), fracture healing, and heterotopic ossification (HO) formation.

3. Study design

The PERK-2 trial is a phase III randomized controlled multicentre trial with three parallel groups. Eligible participants were assigned to receive Ketotifen Fumarate 2 mg, Ketotifen Fumarate 5 mg, or a lactose placebo in a 1:1:1 ratio. Eligible participants will be recruited at fifteen centers across North America.

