5. Outcome measures

The primary endpoint examines whether at least one of the treatment arms (Ketotifen Fumarate 2 mg or 5 mg) is superior to placebo by comparing the mean difference in injured and contralateral elbow flexion-extension arc ROM at Week 12 (Table 1). The secondary endpoints will compare the mean change for multiple range of motion elements from Week 2 to other time points (Week 6, Week 12, Week 24, and Week 52) to establish Ketotifen Fumarate's efficacy over placebo. Other secondary endpoints will compare the mean difference in patients' reported outcome measures (PROMs) at multiple time points. Also, we will combined the two Ketotifen groups and compare it with placebo for the secondary endpoints. The safety assessment will compare the proportion of patients who experienced adverse effects (AEs), serious adverse effects (SAEs), suspected unexpected serious adverse reaction (SUSAR), nonunion and heterotopic ossification, and reoperation in each arm. Table 1 presents a summary of the study's objectives.

Table 1: Objectives and Endpoints

| Study Objectives | Endpoints | | | |
|---|--|--|--|--|
| | Primary | | | |
| Improvement in elbow range of motion. | The mean difference injured and contralateral elbow flexion-extension arc range of motion at Week 12. | | | |
| Socondary | | | | |
| Improvement in elbow range of motion (injured vs. contralateral elbow) at Week 12 | The mean difference injured and contralateral elbow at Week 12 for the following range of motion elements: i. Flexion ii. Pronation iii. Extension iv. Supination | | | |
| 2. Improvement in elbow range of motion from Week 2 to other timepoints | The mean changes from Week 2 to another timepoint (Week 6, Week 12, Week 24, and Week 52) for the following range of motion elements of the injured elbow:i.Flexion-extension arcii.Pronation- supination arciii.Flexioniv.Pronationv.Extensionvi.Supination | | | |
| 3. Improvement in health-related quality of life at Week 12 | The mean difference for the following health-related quality of life measures at Week 12 i. The Disability of the Arm, Shoulder, and Hand (DASH) ii. The Pain Catastrophizing Scale (PCS)) iii. The Oxford Elbow Score (OES) | | | |
| Improvement in health-related quality of life from Week 2 to other timepoints | Mean changes from Week 2 to another timepoint (Week 6, Week 12, Week 24, and Week 52) for the following health-related quality of life measures: | | | |

Alberta Health Services

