| The mean difference between injured and contralateral elbow supination at Week 12 | The data will be analyzed with or without adjusting for specific baseline covariates. The statistical models are described below: a) Linear regression model This model will be used to obtain the unadjusted mean difference between injured and contralateral supination at Week 12. b) The mixed-effects linear regression model This model will be used to obtain the adjusted mean difference between injured and contralateral supination at Week 12. b) The mixed-effects linear regression model This model will be used to obtain the adjusted mean difference between injured and contralateral supination at Week 12. The baseline covariates sex, age, side of injury is the same as the dominant hand, type of elbow injury, and concurrent injury will be regarded as fixed variables, and site as a random variable. Type of elbow injury is defined as AO/OTA classification, i.e., distal humerus vs. proximal radius and ulna. | The mean difference and its corresponding 95% confidence intervals for both the unadjusted and adjusted analysis |

| Study Endpoint | Statistical Model | Es | timate of treatment effects |
|-------------------------------|--|----|---|
| The mean change in flexion- | The data will be analyzed using | • | ANCOVA: The p-value. |
| extension arc of the injuired | a) Analysis of Covariance (ANCOVA) | | |
| elbow from Week 2 to Week 52 | This model will be used to assess the mean difference in flexion-extension arc between Week 2 and Week 52 among the treatment groups after adjusting for flexion-extension arc at Week 2 (baseline value). The model will have Dependent variable: The flexion-extension arc at Week 52 Independent variable: Treatment group Covariate: Flexion-extension arc at Week 2, sex, age, side of injury is the same as the dominant hand, type of elbow injury, and concurrent injury will be regarded as fixed variables, and site as a random variable. Type of elbow injury is defined as AO/OTA classification, i.e., distal humerus vs. proximal radius and ulna. | - | Mixed-effect linear regression model: The mean difference and its corresponding 95% confidence intervals |

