| | b) Mixed-effects linear regression model This model will be used to account for correlation among observations and estimate the effect of covariates on repeated outcomes. It will use the flexion- extension arc recorded at all time points. Also, the baseline covariates sex, age, side of injury is the same as the dominant hand, type of elbow injury, and concurrent injury will be regarded as fixed variables, and site as a random variable. Type of elbow injury is defined as AO/OTA classification, i.e., distal humerus vs. proximal radius and ulna. | | |

| Study Endpoint | Statistical Model | Estimate of treatment effects |
|--------------------------------|--|--|
| The mean change in flexion of | The data will be analyzed using | ANCOVA: The p-value. |
| the injuired elbow from Week 2 | a) Analysis of Covariance (ANCOVA) | |
| to Week 52 | This model will be used to assess the mean difference in flexion arc between Week 2 and Week 52 among the treatment groups after adjusting for flexion arc at Week 2 (baseline value). The model will have Dependent variable: The flexion arc at Week 52 Independent variable: Treatment group Covariate: Flexion arc at Week 2, sex, age, side of injury is the same as the dominant hand, type of elbow injury, and concurrent injury will be regarded as fixed variables, and site as a random variable. Type of elbow injury is defined as AO/OTA classification, i.e., distal humerus vs. proximal radius and ulna. | Mixed-effect linear regression model: The mean difference and its corresponding 95% confidence intervals |
| | b) Mixed-effects linear regression model This model will be used to account for correlation among observations and estimate the effect of covariates on repeated outcomes. It will use the flexion arc recorded at all time points. Also, the baseline covariates sex, age, side of injury is the same as the dominant hand, type of elbow injury, and concurrent injury will be regarded as fixed variables, and site as a random variable. Type of elbow injury is defined as AO/OTA classification, i.e., distal humerus vs. proximal radius and ulna. | |

| Study Endpoint | Statistical Model | Estimate of treatment effects |
|---|---|--|

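### The repeated-measures model for the Week 2 to Week 52 secondary endpoints names only site as random and lists no participant, visit or arm-by-visit term

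*SAP*

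**What the plan says.** SAP Section 5 defines these secondary endpoints as mean change "from Week 2 to other time points (Week 6, Week 12, Week 24, and Week 52"). Section 7.2, Table 2, gives each Week 2 to Week 52 row two analyses. There are eight such rows: flexion-extension arc, flexion, extension, pronation, supination, DASH, PCS and OES.

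- **Model (a), ANCOVA.** The Week 52 value is the dependent variable and the Week 2 value a covariate. Its listed output is "ANCOVA: The p-value".
- **Model (b), mixed-effects regression.** Its purpose is stated as "This model will be used to account for correlation among observations and estimate the effect of covariates on repeated outcomes". On the data, the first of these rows says: "It will use the flexion- extension arc recorded at all time points". After listing sex, age, dominant side and injury type, the text ends: "and concurrent injury will be regarded as fixed variables, and site as a random variable". Its listed output is "Mixed-effect linear regression model: The mean difference and its corresponding 95% confidence intervals".

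None of the eight rows names a participant effect, a within-participant covariance structure, a visit term or an arm-by-visit term. The same fixed-and-random wording appears in the Week 12 rows, where each participant has one value.

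**The concern.** Once several visits enter the model, each participant contributes several rows, and the correlation that matters most is among one person's own measurements. A site intercept captures only what everyone at a centre has in common. The one random term named therefore does not achieve the stated purpose.

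Two things are at stake. The first is whether the interval around the reported difference has its nominal coverage. The second is what that difference estimates: without an arm-by-visit term it is an average over visits, whereas Section 5 asks for change from Week 2 to each named visit. In Table 2 the ANCOVA supplies only a p-value, so the tabulated estimate and interval for these endpoints come from model (b).

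**Working it through.** **Inputs from the SAP.** Visits are Weeks 2, 6, 12, 24 and 52 (Section 5), so m = 5, or m = 4 if Week 2 is not an outcome row. The SD is 25°, with 127 per arm and 11% dropout (Section 4), so 127 × 0.89 = 113 evaluable per arm. There are fifteen centres (Section 3). The SAP states no figure for this model's precision, so there is none to reproduce.

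**Assumptions.** Within-person correlation ρ is 0.3, 0.5 or 0.7, equal for all pairs of visits. The 25° is used as the SD at each visit. Visit means are taken as equal or fitted.

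**Step 1: coverage of the visit-averaged arm effect.** Ignoring ρ understates the variance by DE = 1 + (m − 1)ρ. True coverage of a nominal 95% interval is 2Φ(1.96/√DE) − 1. If Week 2 is a covariate, the correlation left among the four later visits is ρ/(1 + ρ) = 0.23, 0.33 or 0.41.

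| Case | DE | √DE | Coverage |
|---|---|---|---|
| m = 5, ρ = 0.3 / 0.5 / 0.7 | 2.2 / 3.0 / 3.8 | 1.48 / 1.73 / 1.95 | 81.4% / 74.2% / 68.5% |
| m = 4, same ρ | 1.9 / 2.5 / 3.1 | 1.38 / 1.58 / 1.76 | 84.5% / 78.5% / 73.4% |
| m = 4, Week 2 as covariate | 1.69 / 2.00 / 2.24 | 1.30 / 1.41 / 1.50 | 86.8% / 83.4% / 81.0% |

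In degrees, with m = 5, the half-width ignoring ρ is 1.96 × 25 × √(2/(113 × 5)) = 2.9° at every ρ. Multiplying by √DE gives 4.3°, 5.1° and 5.7°.

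**Step 2: simulation.** The set-up was 15 sites, 339 participants, 5 visits, SD 25°, an assumed site correlation of 0.03, a fitted visit term and 300 runs per ρ. The random-site-only model covered 80%, 76% and 65%. An analysis at participant level covered 94%, 95% and 93%. Simulation error is about √(0.75 × 0.25/300) = 2.5 points near 75% coverage, so this agrees with Step 1.

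**Step 3: what the average estimates (illustrative arm differences at the five visits).**

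- 0, 2.5, 5, 7.5, 10: the average is 25/5 = 5, and the difference in change from Week 2 to Week 52 is 10 − 0 = 10.
- 0, 5, 10, 10, 10: the average is 35/5 = 7, and the difference in change is 10.
- 2, 5, 10, 8, 5: the average is 30/5 = 6, and the difference in change is 5 − 2 = 3.

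The average can fall on either side of the endpoint.

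**Step 4: adding only an arm-by-visit term.** For change between two visits, the true variance is proportional to 2(1 − ρ), but a model without a participant term uses 2. The ratio of true to reported standard error is √(1 − ρ) = 0.84, 0.71 and 0.55. The interval is then too wide, with coverage of 98.1%, 99.4% and nearly 100%. The two terms have to be added together.

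**The case against.** The strongest reply is that the list of terms is not exhaustive. Treatment is not listed in model (b) either, yet it must be there. The covariates and site are introduced as additions to a model already said to handle correlation, so a within-participant structure may well have been intended. This stands, and it limits the point. A reader might infer that the SAP prescribes a model with no participant effect and that its intervals are therefore wrong. The text supports only that the structure is left unspecified and that the one random term named is not the one repeated measures need. Intent does not choose between a random intercept and an unstructured covariance, and it does not supply the arm-by-visit contrast.

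A reader might also turn the coverage shortfall into a type I error of 18.6% to 31.5% (100% minus coverage, five visits). Table 2 assigns the p-value to the ANCOVA, which uses one Week 52 value per participant, so that test does not have this problem. Only interval coverage is at issue.

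Nor are intervals too narrow in every case: that direction holds for the visit-averaged effect and reverses for change from Week 2. Nor is model (b) the only source of intervals in the SAP, because Section 7.1 also promises intervals for group differences in its descriptive analysis.

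Finally, the size depends on a correlation the SAP does not give, and on visit means being equal or fitted. Without a visit term, recovery over time would enter the residual and widen the interval, partly offsetting the shortfall.

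**Conclusion.** The point holds as a specification fault in a secondary analysis. As named, the terms of model (b) do not deliver its stated purpose, and its single output is not the change from Week 2 that Section 5 defines. If fitted with the named terms plus treatment, and with visit means equal or fitted, the nominal 95% interval for the visit-averaged effect would cover about 81% to 69% with five visits. With four visits it would cover 85% to 73%, and with Week 2 as a covariate 87% to 81%. All of these assume a within-person correlation of 0.3 to 0.7. The mismatch in what is estimated does not depend on that correlation. It arises in general when the treatment effect varies over visits, and the ANCOVA p-value and the interval beside it could then point to different conclusions.

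A reader might extend this to the primary result. The SAP does not support that: the primary Week 12 analysis has one value per participant and is unaffected.

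**What to change.** In all eight rows, state model (b) in full:

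- fixed effects for treatment, visit and treatment-by-visit, plus the covariates already listed;
- site as random;
- a participant-level term: unstructured within-participant covariance, with a participant random intercept as the named fallback if that does not converge.

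From this model, report for each dose versus placebo the difference in change from Week 2 to Weeks 6, 12, 24 and 52, with 95% intervals. Each is the arm difference at that visit minus the arm difference at Week 2. Estimate, interval and p-value then address the same endpoint.

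The cost is SAP wording and a slightly larger model, with no new data. Interval widths will change, and some may be wider.

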| The mean change in extension arc of the injuired elbow from Week 2 to Week 52 | The data will be analyzed using Analysis of Covariance (ANCOVA) This model will be used to assess the mean difference in extension arc between Week 2 and Week 52 among the treatment groups after adjusting for extension arc at Week 2 (baseline value). The model will have Dependent variable: The extension at Week 52 | ANCOVA: The p-value. Mixed-effect linear regression model: The mean difference and its corresponding 95% confidence intervals |
| | Independent variable: Treatment group Covariate: Extension arc at Week 2, sex, age, side of injury is the same as the dominant hand, type of elbow injury, and concurrent injury will be regarded as fixed variables, and site as a random variable. Type of elbow injury is defined as AO/OTA classification, i.e., distal humerus vs. proximal radius and ulna. | |
| | b) Mixed-effects linear regression model This model will be used to account for correlation among observations and estimate the effect of covariates on repeated outcomes. It will use the extension arc recorded at all time points. Also, the baseline covariates sex, age, side of injury is the same as the dominant hand, type of elbow injury, and concurrent injury will be regarded as fixed variables, and site as a random variable. Type of elbow injury is defined as AO/OTA classification, i.e., distal humerus vs. proximal radius and ulna. | |

| Study Endpoint | Statistical Model | Estimate of treatment effects |
|---|--|--|
| The mean change in pronation of the injuired elbow from Week 2 to Week 52 | The data will be analyzed using a) Analysis of Covariance (ANCOVA) This model will be used to assess the mean difference in pronation between Week 2 and Week 52 among the treatment groups after adjusting for pronation arc at Week 2 (baseline value). The model will have | ANCOVA: The p-value. Mixed-effect linear regression model: The mean difference and its corresponding 95% confidence intervals |
| | Dependent variable: The pronation at Week 52 Independent variable: Treatment group Covariate: pronation at Week 2, sex, age, side of injury is the same as the dominant hand, type of elbow injury, and concurrent injury will be regarded as fixed variables, and site as a random variable. Type of elbow injury is defined as AO/OTA classification, i.e., distal humerus vs. proximal radius and ulna. | |

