| | b) Mixed-effects linear regression model This model will be used to account for correlation among observations and estimate the effect of covariates on repeated outcomes. It will use the pronation recorded at all time points. Also, the baseline covariates sex, age, side of injury is the same as the dominant hand, type of elbow injury, and concurrent injury will be regarded as fixed variables, and site as a random variable. Type of elbow injury is defined as AO/OTA classification, i.e., distal humerus vs. proximal radius and ulna. | |

| Study Endpoint | Statistical Model | Estimate of treatment effects |
|--|--|--|
| The mean change in supination of the injuired elbow from Week 2 to Week 52 | The data will be analyzed using a) Analysis of Covariance (ANCOVA) This model will be used to assess the mean difference in supination between Week 2 and Week 52 among the treatment groups after adjusting for supination at Week 2 (baseline value). The model will have | ANCOVA: The p-value. Mixed-effect linear regression model: The mean difference and its corresponding 95% confidence intervals |
| | Dependent variable: The supination at Week 52 Independent variable: Treatment group Covariate: Supination arc at Week 2, sex, age, side of injury is the same as the dominant hand, type of elbow injury, and concurrent injury will be regarded as fixed variables, and site as a random variable. Type of elbow injury is defined as AO/OTA classification, i.e., distal humerus vs. proximal radius and ulna. | |
| | b) Mixed-effects linear regression model This model will be used to account for correlation among observations and estimate the effect of covariates on repeated outcomes. It will use the flexion- extension arc recorded at all time points. Also, the baseline covariates sex, age, side of injury is the same as the dominant hand, type of elbow injury, and concurrent injury will be regarded as fixed variables, and site as a random variable. Type of elbow injury is defined as AO/OTA classification, i.e., distal humerus vs. proximal radius and ulna. | |

| Study Endpoint | Statistical Model | Estimate of treatment effects |
|--|---|--|

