| | b) The mixed-effects linear regression model This model will be used to obtain the adjusted mean difference in OES score at Week 12. The baseline covariates sex, age, side of injury is the same as the dominant hand, type of elbow injury, and concurrent injury will be regarded as fixed variables, and site as a random variable. Type of elbow injury is defined as AO/OTA classification, i.e., distal humerus vs. proximal radius and ulna. | |

| Study Endpoint | Statistical Model | Estimate of treatment effects |
|---|--|--|
| The mean change in DASH score from Week 2 to Week 52 | The data will be analyzed using a) Analysis of Covariance (ANCOVA) This model will be used to assess the mean difference in DASH score between Week 2 and Week 52 among the treatment groups after adjusting for DASH score at Week 2 (baseline value). The model will have | ANCOVA: The p-value. Mixed-effect linear regression model: The mean difference and its corresponding 95% confidence intervals |
| | Dependent variable: The DASH score at Week 52 Independent variable: Treatment group Covariate: DASH score at Week 2, sex, age, side of injury is the same as the dominant hand, type of elbow injury, and concurrent injury will be regarded as fixed variables, and site as a random variable. Type of elbow injury is defined as AO/OTA classification, i.e., distal humerus vs. proximal radius and ulna. | |
| | b) Mixed-effects linear regression model This model will be used to account for correlation among observations and estimate the effect of covariates on repeated outcomes. It will use the DASH score recorded at all time points. Also, the baseline covariates sex, age, side of injury is the same as the dominant hand, type of elbow injury, and concurrent injury will be regarded as fixed variables, and site as a random variable. Type of elbow injury is defined as AO/OTA classification, i.e., distal humerus vs. proximal radius and ulna. | |

| Study Endpoint | Statistical Model | Estimate of treatment effects |
|--|---|--|

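### In the SAP Table 2 row for change in supination from Week 2 to Week 52, the mixed-effects model names the flexion-extension arc as its data

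*SAP*

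**What the plan says.** Table 2 in SAP section 7.2 gives each endpoint a row with its model or models and the quantities to be reported. The row at issue is headed "The mean change in supination of the injuired elbow from Week 2 to Week 52". It specifies two models.

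- **Model (a), ANCOVA.** The outcome is supination: "Dependent variable: The supination at Week 52 Independent variable: Treatment group". The baseline covariate is supination at Week 2.
- **Model (b), mixed-effects linear regression.** This is the repeated-measures model. The data it is to use are given in one sentence: "It will use the flexion- extension arc recorded at all time points".

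The last column of the row divides the reporting between the two models: "ANCOVA: The p-value. Mixed-effect linear regression model: The mean difference and its corresponding 95% confidence intervals".

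The sentence in model (b) occurs twice in Table 2, once in the flexion-extension arc row and once in the supination row. This point concerns only the second occurrence.

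**The concern.** The sentence in model (b) is the only place in the row that tells the analyst which repeated measurements enter the mixed model. It names a different movement from the one in the row's title. The SAP treats the two as distinct: in Table 1, flexion-extension arc and supination are separate items in the list of elements whose change from Week 2 is assessed.

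The way the row splits its reporting adds to the problem. If both models produced an estimate, a wrong variable in one would show up as a disagreement with the other. Here the ANCOVA contributes a p-value only, and the effect size and its interval come solely from the mixed model. A literal implementation would therefore give one line of results in which the p-value refers to supination and the mean difference and 95% confidence interval refer to the flexion-extension arc. Nothing in the output would reveal the mismatch, because both are measured in degrees and both would look plausible.

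The reach also goes somewhat beyond Week 52. Table 1 lists change from Week 2 to Weeks 6, 12, 24 and 52. The ANCOVA in this row has Week 52 as its outcome, so the mixed model is the only one of the two that draws on the intermediate visits.

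**Working it through.** No arithmetic is involved beyond a count. The question is which variable each row names, and it does not depend on alpha, power, effect size, standard deviation or dropout.

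**Step 1: compare the rows.** Eight rows of Table 2 analyse change from Week 2 to Week 52. Each has a model (b) with a parallel sentence naming the repeated outcome.

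| Endpoint of the row | What model (b) is told to use | Agrees with the row? |
|---|---|---|
| Flexion-extension arc | Flexion-extension arc (same sentence as in the supination row) | Yes |
| Flexion | "It will use the flexion arc recorded at all time points" | Yes |
| Extension | "It will use the extension arc recorded at all time points" | Yes |
| Pronation | "It will use the pronation recorded at all time points" | Yes |
| Supination | "It will use the flexion- extension arc recorded at all time points" | **No** |
| DASH | "It will use the DASH score recorded at all time points" | Yes |
| PCS | PCS score | Yes |
| OES | OES score | Yes |

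Count: 7 of 8 agree, and 8 − 7 = 1 does not. Naming the row's own endpoint is therefore the convention of the table, and the supination row is the only exception.

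**Step 2: read within the supination row.** The title, the description of the ANCOVA, its dependent variable and its Week 2 covariate all say supination. Only the sentence in model (b) says otherwise. The row contradicts itself, and everything else in it points to supination as the intended variable.

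**Step 3: identify the likely source.** The sentence matches the one in the flexion-extension arc row word for word. It is complete and readable in both places, so it is not a broken table cell or a redaction. A carry-over from the earlier row is the natural explanation.

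**Step 4: trace the consequence through the reporting column.**

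- ANCOVA on supination gives the p-value for supination.
- The mixed model on the flexion-extension arc gives the mean difference and 95% confidence interval for the flexion-extension arc.

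Since model (b) carries the same covariates and the same random site term in both rows, the estimate and interval printed for supination would repeat those of the flexion-extension arc row.

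**Step 5: check what else the SAP provides for supination.**

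- Table 2 has a separate row for injured versus contralateral supination at Week 12. It has an unadjusted linear regression and an adjusted mixed model, each reporting a mean difference and 95% confidence interval. Both name supination.
- Section 7.1 provides for point estimates with two-sided 95% confidence intervals for group differences as part of the descriptive analysis of the endpoints.

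Neither is touched by the error. Neither is the covariate-adjusted, repeated-measures estimate that the change row is meant to deliver.

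**The case against.** The strongest reply is that this is a plain copying slip and that nobody would act on it. The row's title, its ANCOVA and Table 1 all say supination, and the seven parallel rows show what was meant. An analyst would have to report a variable that contradicts the heading of the row. Only one of many secondary endpoints is involved.

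Most of that stands. The intended variable is not in real doubt, and the harm arises only under a literal reading. This limits the importance of the point but does not remove the need for a correction. Table 2 is the specification that programs are written from, and the outcome variable of a planned model should be right before results are seen. If the analyst quietly substitutes supination, the analysis will be sensible but will depart from the written plan with no record of why.

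A reader might infer two stronger things, and the SAP supports neither:

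- **That supination would have no effect estimate at all, or that the endpoint is lost.** The Week 12 supination row and the descriptive estimates in section 7.1 both survive a literal reading. What would be misdirected is the model-based estimate in one row.
- **That the sponsor chose to analyse supination through the flexion-extension arc.** Nothing in the SAP argues for this, and the ANCOVA in the same row contradicts it. It is an inconsistency, not a choice of method.

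**Conclusion.** The point holds, within narrow limits. The supination change row contains an operative instruction that is wrong as written. If it were followed to the letter, the model-based mean difference and 95% confidence interval for that one secondary endpoint would describe the flexion-extension arc, while the p-value beside them would describe supination.

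The extent is one sentence in one of eight parallel rows. The primary endpoint and its analysis, the sample size, the safety analyses, the Week 12 supination comparison and the descriptive estimates are unaffected. The conclusion rests on two readings of the SAP: that the sentence in model (b) defines the outcome of the mixed model, as it does in the other seven rows, and that the reporting column means what it says about which model supplies the estimate. It is a minor inconsistency, but it sits in an analysis instruction and should be corrected before the analysis is run.

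**What to change.** In Table 2, in the row for change in supination from Week 2 to Week 52, model (b), replace the sentence naming the flexion-extension arc with: *It will use the supination recorded at all time points.*

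The correction should identify the row explicitly. The identical sentence in the flexion-extension arc row is right and must stay, so a search-and-replace across the table would introduce a new error. If analysis programs have already been written from Table 2, the outcome variable in the supination mixed model should be checked at the same time.

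The cost is one line of SAP wording. The change needs no new data and leaves the design, the sample size and every other analysis as they are.
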